8.2. Prophylactic Immune Tolerance Induction (ITI) Regimen

To prevent the risks of an inflammatory response and to protect AAV-transduced cells from immune response to the AAVrh8 capsid and/or transgene, participants will be immunosuppressed prior to administration of AXO-AAV-GM2 treatment. The ITI regimen will be maintained as described below.

Starting on Day -7 of the study, the following will be initiated:

- Rituximab* at 375 mg/m² BSA (IV infusion)
 - *Pre-medication for rituximab infusion will include:
 - acetaminophen 10-15 mg/kg given either PO, g-tube or rectal one time prior to infusion (may repeat q 4 hours for temperature >38.3°C)
 - diphenhydramine 1 mg/kg given either PO, g-tube or IV one time prior to infusion (may repeat 1 mg/kg IV PRN)
- Solu-Medrol at 10 mg/kg (IV infusion)
- Sirolimus* at 1.5 mg/m² BSA/day (PO or by feeding tube) *adjustment permitted to achieve trough levels of 7-12 ng/mL
- Prednisolone at 1-2 mg/kg/day (PO or by feeding tube)
- Lansoprazole at 1-1.5 mg/kg/day (PO or by feeding tube)
- Trimethoprim/sulfamethoxazole 2.5 mg/kg/day BID on 2 consecutive days per week (PO or by feeding tube) or per PI discretion

Day -2, Day 1 (BiTh Infusion Day), Day 2 (ICM/IT Infusion Day):

• Rituximab* at 375 mg/m² BSA (IV infusion), as needed for persistent CD20 count ≥ 5%

*Pre-medication for rituximab infusion will include:

- acetaminophen 10-15 mg/kg given either PO, g-tube or rectal one time prior to infusion (may repeat q 4 hours for temperature >38.3°C)
- diphenhydramine 1 mg/kg given either PO, g-tube or IV one time prior to infusion (may repeat 1 mg/kg IV PRN)
- Continuation of sirolimus*, prednisolone, and lansoprazole dosing (PO or by feeding tube)
 - *adjustment permitted to achieve trough levels of 7-12 ng/mL
- Continuation of trimethoprim/sulfamethoxazole 2.5 mg/kg/day BID on 2 consecutive days (PO or by feeding tube) or per PI discretion

Day 2-8:

- Continuation of sirolimus*, prednisolone, and lansoprazole dosing (PO or by feeding tube)
 - *adjustment permitted to achieve trough levels of 7-12 ng/mL
- Continuation of trimethoprim/sulfamethoxazole 2.5 mg/kg/day BID on 2 consecutive days per week (PO or by feeding tube) or per PI discretion

Confidential Page 40 of 97

Clinical Study Protocol: AXO-GM2-001

Version 8.0, 09 June 2023

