Lansoprazole 18			X	X	X	X	X	X	X	X	X	X	X	X						
IVIG administration 19						AN				AN	AN	AN	AN	AN			AN			
Bilat Intrathalamic Infusion					X															
Intrathecal Infusion						X														
LP CSF collection 20	X					X								X			X	X ²⁷	X ²⁷	X ²⁷
CSF HexA activity level, GM2 ganglioside	X					X								X			X	X ²⁷	X ²⁷	X ²⁷
Sirolimus levels			AN	X	Х	AN	X	X	X	X	X	X	X	X			AN			
Anti-seizure drug levels 21		AN	AN	AN	AN	AN	AN	AN	AN	AN	AN	AN	AN	AN	AN	AN	AN	AN	AN	AN
Adverse Events review		X	X	X	X	X	X	X	X	X	X	X	X	X	X	X	X	X	X	X
Concomitant medication review		X	X	X	X	X	X	Х	X	X	X	X	X	X	X	X	X	X	X	X

Footnotes:

- 1. Verification of *HEXA* or *HEXB* gene mutation and modifiers by reports
- 2. Measurements include systolic and diastolic blood pressure, pulse rate per minute, respiratory rate per minute, and temperature
- 3. Comprehensive exam or limited exam at the discretion of the clinician based on status of the participants. Exams may be videotaped. For Visit 1b (Day 2), perform neurologic checks every 2h for the first 24h, and full physical and neurological exam 24h, 48h, and 72h post infusion.
- 4. Safety labs will be prioritized based on the participant's conditions at the discretion of the investigator. Additional safety labs may be required for participant management. Safety labs include the following: CBC with auto-differential and comprehensive metabolic panel, AST, ALT, ALP repeated as needed if 2X baseline, ELISpot. A CH50 may also be performed as clinically indicated, i.e., platelet count decrease. Additionally, PT, PTT, and INR will be assessed prior to surgery.
- 5. Infectious disease testing will be performed as clinically indicated (i.e., based on Medical History) and will include HIV, hepatitis A, B and C, herpes simplex virus, cytomegalovirus, Epstein Barr virus, varicella zoster virus, and toxoplasmosis
- 6. IgG levels to be done at least 3 days prior to the scheduled visit, at a local lab as necessary. Performed as needed at month 6, contingent on results from month 3

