- 25. Participants must have a swallow evaluation test performed within 6 months prior to AXO-AAV-GM2 administration to assess the risk of aspiration. If aspiration risk is identified, it must be clinically managed prior to surgical procedures. Participants must have a swallow evaluation test performed at baseline and a clinical assessment of swallowing and a swallow study, if warranted, at Visit 9 (Week 12), Visit 12 (Week 24), Visit 13 (Week 48), Visit 15 (Week 96) and yearly thereafter for Years 3-5 (see Table 16).
- 26. BAER/VER/SSEP should be conducted without sedation or a prolongation of, or another episode of general anesthesia.
- 27. May be completed if visit occurs in person however not if the visit is completed as a tele-health
- 28. Tele-health will occur if Pt does not come to site in person

AN - As Needed

Confidential Page 57 of 97

Clinical Study Protocol: AXO-GM2-001

Version 8.0, 09 June 2023

Confidential Page 58 of 97

Clinical Study Protocol: AXO-GM2-001

Version 8.0, 09 June 2023

 Table 15:
 Schedule of Infantile-Onset Participant Assessments

Schedule of Activities	Visit A	Visit B	Visit C	Visit D	Visit 1a	Visit 1b	Visit 2	Visit 3	Visit 4	Visit 5	Visit 6	Visit 7	Visit 8	Visit 9	Visit 10	Visit 11	Visit 12	Visit 13
	Week - 8	Day -16	Day -7	Day -2	Day	Day	Day	Day	Day	Week	Week	Week	Week	Week	Week	Week	Week	Week
	±28d	±5d	±3d	-2 ±1d	-	2	8 ±1d	15 ±3d	22 ±3d	4 ±3d	6 ±4d	8 ±5d	10 ±4d	12 ±7d	16 ±7d	20 ±7d	24 ±7d	48 ±7d
ICF	X*	Х																
Inclusion/Exclusion Criteria	X*	Х																
Genetic Confirmation ¹	X*																	
Vital Signs 11	X*	Х	X	X	Х	X	X	X	X	X	X	X	X	X			X	X ²³
Weight	X*	X	X	X			X	X	X	X	X	X	X	X			X	X ²³
Height	X*	X	X											X			X	X ²³
Physical Examination	X*	X		X	X	X	X	X	X	X	X	X	X	X			X	X ²³
Neurologic Examination ¹²	X*			X		X	X	X	X	X	X	X	X	X			X	X ²³
Tele-health follow-up															X	X		X ²⁴
Tele-health Neuro Exam																		X ²⁴
Ophthalmology Exam			X															
HINE-2	X*									X				X			X	X ²³
BSID-III	X*									X				X			X	X ²³
Clinical Global Impression	X*									X				X			X	X
CBC with auto-differential ⁶	X				X	X	X	X	X	X	X	X	X	X			X	X ²³
Comprehensive metabolic panel ⁶	Х				Х	Х	X	Х	X	X	Х	Х	X	Х			X	X ²³
hsCRP	X				X	X	X	X	X	X	X	X	X	X			X	X ²³
GGT – AN due to elevated liver enzymes	AN				AN	AN	AN	AN	AN	AN	AN	AN	AN	AN			AN	AN
PT, PTT, INR, Blood Typing ⁶				X														
Total hemolytic complement (CH50) – AN due to platelet count decrease ⁶	AN				AN	AN	AN	AN	AN	AN	AN	AN	AN	AN			AN	AN

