Serum HexA activity level	X					X			X	X		X		X			X	X ²³

Page 59 of 97

Clinical Study Protocol: AXO-GM2-001

Version 8.0, 09 June 2023

 Table 15:
 Schedule of Infantile-Onset Participant Assessments (Continued)

Schedule of Activities	Visit A	Visit B	Visit C	Visit D	Visit la	Visit 1b	Visit 2	Visit 3	Visit 4	Visit 5	Visit 6	Visit 7	Visit 8	Visit 9	Visit 10	Visit 11	Visit 12	Visit 13
	Week	Day -16	Day -7	Day -2	Day 1	Day 2	Day 8	Day 15	Day 22	Week 4	Week 6	Week 8	Week 10	Week 12	Week 16	Week 20	Week 24	Week 48
	±28d	±5d	±3d	±1d	1	1	±1d	±3d	±3d	±3d	±4d	±5d	±4d	±7d	±7d	±7d	±7d	±7d
Sirolimus levels			AN	X	X	AN	X	X	X	X	X	X	X	X			AN	
Anti-seizure drug levels ⁷		AN	AN	AN	AN	AN	AN	AN	AN	AN	AN	AN	AN	AN	AN	AN	AN	AN
CD 19, 20 count		X	X	X		AN				X		X		X			AN	AN
IgA level			X															
IgG levels ⁸				X						X		X		X			AN	AN
Research blood collection 9		X		X			X	X	X	X	X	X	X	X			X	X ²³
Anti-AAVrh8 antibodies (ADA) ⁹		X		X			X	X	X	X	X	X	X	X			X	X^{23}
Transgene antibodies (ADA) ⁹		X		X			X	X	X	X	X	X	X	X			Х	X ²³
Neutralizing antibodies (Nabs) ⁹		X		X			X	X	X	X	X	X	X	X			X	X ²³
GM2 ganglioside levels (serum) ⁹		X		X			X	X	X	X	х	X	X	X			X	X^{23}
ELISpot		X		AN			X	X	X	X	X	X	X	X			X	X^{23}
Infectious disease testing ¹⁰ – As clinically indicated based on Medical History		AN																
Urinalysis					X									AN			AN	AN
Chest X-ray		X																
Swallow Study ²²		Х												X			X	X ²³
ECG		Х			AN		AN	AN	AN	AN	AN	AN	AN	X			AN	X ²³
EEG ²		Х							X									
Echocardiogram ³		Х																
Pre-Surgical MRI /CT ⁴			X															
Intra-surgical CT					Х													

Page 60 of 97

Clinical Study Protocol: AXO-GM2-001

Version 8.0, 09 June 2023

 Table 15:
 Schedule of Infantile-Onset Participant Assessments (Continued)

Schedule of Activities	Visit A	Visit B	Visit C	Visit D	Visit 1a	Visit 1b	Visit 2	Visit 3	Visit 4	Visit 5	Visit 6	Visit 7	Visit 8	Visit 9	Visit 10	Visit 11	Visit 12	Visit 13
	Week	Day -16	Day -7	Day -2	Day 1	Day 2	Day 8	Day 15	Day 22	Week 4	Week 6	Week 8	Week 10	Week 12	Week 16	Week 20	Week 24	Week 48
	±28d	±5d	±3d	±1d	-	-	±1d	±3d	±3d	±3d	±4d	±5d	±4d	±7d	±7d	±7d	±7d	±7d
Post-Surgical MRI					X													
MRI, MRS, DTI 5	X													X			X	X ²³
Surgical readiness determination		X																
Central Venous Catheter placement 13		AN	AN	AN														
Rituximab infusion 14			X	AN														
Solu-Medrol infusion 15			X															
Sirolimus 16			X	X	X	X	X	X	X	X	X	X	X	X	X	X	wean	

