- 9. Blood will be collected for research as tolerated by the participant and will be frozen for later use or used for the isolation of serum or PBMCs. The amount of research blood collected, and its intended use, will vary between visits based on the overall volume of blood collected within a 1-week period remaining < 10 mL. Sample prioritization will be determined by investigator and Sponsor if collected blood volume is limited. Collect blood on Visit B (Day -16) prior to immunosuppression.. Blood collected for research can include anti-AAVrh8 antibodies (ADA), transgene antibodies (ADA) and neutralizing antibodies (Nabs) if needed. The priority should be the antibodies followed by the serum HEXA activity and then GM2 ganglioside levels in serum.
- 10. Infectious disease testing will be performed as clinically indicated (i.e., based on Medical History) and will include HIV, hepatitis A, B and C, herpes simplex virus, cytomegalovirus, Epstein Barr virus, varicella zoster virus, and toxoplasmosis
- 11. Measurements include systolic and diastolic blood pressure, pulse rate per minute, respiratory rate per minute, and temperature
- 12. Comprehensive exam or limited exam at the discretion of the clinician based on participant's status. Exams may be videotaped. For Visit 1b (Day 2), perform neurologic checks every 2h for the first 24h, and full physical and neurological exam 24h, 48h, and 72h post infusion while inpatient.
- 13. Caregivers will have option to have central venous catheter inserted into participants prior to surgical gene transfer to ensure venous access and reduce difficulty and pain associate with blood draws during the study
- 14. Rituximab IV infusion at 375 mg/m² body surface area (BSA). As needed at Day -2 for persistent CD20 count greater than or equal to 5%
- 15. Solu-Medrol IV infusion at 10 mg/kg
- 16. Sirolimus oral at 1.5 mg/m² BSA; Adjust dose to achieve serum trough levels of 7-12 ng/mL as needed. To be weaned starting Visit 12/Week 24 according to the following regimen: Week 24-25: reduce dose by 50%; Week 25-26: reduce Week 24-25 dose by 50%; Week 26-27: reduce Week 25-26 dose by 50% then stop
- 17. Prednisolone 1-2 mg/kg/day, to be tapered starting Visit 9/Week 12 according to the following regimen: Week 12-13: reduce dose by 50%; Week 13-14: reduce week 12-13 dose by 50%; Week 14-15: reduce week 13-14 dose by 50%; Week 15-16: reduce week 13-14 dose by 50% then stop.

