Participants otherwise eligible for study participation but deemed not currently fit for neurosurgery may be re-screened at the discretion of the investigator

- 5. Participants receiving off-label miglustat and/or Tanganil must be willing to discontinue these therapies 30 days prior to the start of screening
- 6. Ability to reliably travel to the study sites for study visits according to the Schedule of Assessments

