9.2. Participant Exclusion Criteria

- 1. Presence of G269S or W474C mutation in HEXA
- 2. Evidence of lower respiratory tract aspiration not easily manageable with thickening of feedings or substitution of a modified bottle nipple, as judged on a multi-texture contrast swallow.
- 3. History of multiple aspiration pneumonias occurring in the past twelve months.
- 4. Respiratory support in the form of ventilation (invasive or non-invasive).
- 5. History of drug-resistant seizures or status epilepticus
- 6. History and/or findings of spinal cord disease that would preclude the LP and ICM/IT infusion procedures including:
 - Infectious process involving the spinal canal which may cause adhesions or septations in the spinal and/or subarachnoid space
 - Previous spinal surgeries
 - History of trauma, bleeding in the spinal canal
 - Vascular or cystic lesions, or any other mass lesion
 - Congenital deformities and malformations involving the spinal canal
 - Posterior fossa findings (low lying cerebellar tonsils, crowded foramen magnum, small or absent cisterna magna)
- 7. The participant's parent(s) or legal guardian(s) is unable to understand the nature, scope, and possible consequences of the study, or does not agree to comply with the protocol defined schedule of assessments
- 8. Any prior participation in a study in which a gene therapy vector or stem cell transplantation was administered
- 9. Immunizations of any kind in the month prior to screening
- 10. Cardiomyopathy or other cardiac disease (based on echocardiogram and/or ECG) that in the opinion of the Investigator would deem the participant unsafe to undergo surgical gene transfer
- 11. Indwelling ferromagnetic devices that would preclude MRI/ /MRS/DTI imaging
- 12. Ongoing medical condition that is deemed by the Investigator to interfere with the conduct or assessments of the study

Confidential Page 69 of 97

Clinical Study Protocol: AXO-GM2-001

Version 8.0, 09 June 2023

13. Current clinically significant infections including any requiring systemic treatment including but not limited to human immunodeficiency virus (HIV), Hepatitis A, B, or C

- 14. History of or current chemotherapy, radiotherapy or other immunosuppressive therapy within the past 30 days. corticosteroid treatment may be permitted at the discretion of the PI
- 15. Clinically significant laboratory abnormalities:

Based on age-specific reference range and determined by the investigator

- Total WBC count
- Hemoglobin
- Creatinine

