- Pancreatic enzymes

Based on the following thresholds

- Platelet count ($< 150,000/\mu L$)
- Prothrombin (PT), partial thromboplastin time (PTT) >2X normal
- Liver transaminases (Hy's Law: > 3x elevations above the ULN of ALT or AST and serum total bilirubin > 2xULN)
- 16. Participants for whom any of the proposed study procedures or medications (i.e. sirolimus, trimethoprim/sulfamethoxazole) would be contraindicated
- 17. Failure to thrive, defined as falling 20 percentiles (20/100) in body weight in the 3 months preceding Screening/Baseline
- 18. Participant is not suitable for participation in the study in the opinion of the Principal Investigator

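### Exclusion 15 bars PT/PTT above twice normal, but both schedules first test PT/PTT 1 to 9 days after immunosuppression has begun

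*Combined protocol and SAP*

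**What the plan says.** Section 9.2, exclusion 15, lists laboratory abnormalities that exclude a participant. Among those with a fixed threshold is "Prothrombin (PT), partial thromboplastin time (PTT) >2X normal"; the synopsis carries the same item.

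In the juvenile schedule (Table 14) and the infantile schedule (Table 15), the row "PT, PTT, INR, Blood Typing" has a single mark, at Visit D (Day -2 ±1). The inclusion/exclusion row is marked at Visits A (Week -8 ±28 days) and B (Day -16 ±5) only. The safety-laboratory footnote in each table (4 in Table 14, 6 in Table 15) says "Additionally, PT, PTT, and INR will be assessed prior to surgery". It ties the test to surgery and does not mention eligibility or the start of immunosuppression.

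Section 8.2 sets the immune tolerance induction (ITI) regimen: "Starting on Day -7 of the study, the following will be initiated", followed by rituximab 375 mg/m², Solu-Medrol 10 mg/kg, and daily sirolimus and prednisolone. Tables 14 and 15 place these at Visit C (Day -7 ±3).

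Section 8.2 also stops the regimen for bleeding, or for a clinically important rise in clotting measures, when nothing else explains it. A child whose regimen has to be stopped before Day 1 loses eligibility for gene transfer and leaves the study.

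**The concern.** An eligibility threshold should be checked before the child is exposed to anything that eligibility is meant to gate. Section 9.1 follows this logic for function: the required abilities are confirmed at screening and checked again before immunosuppression. Most of exclusion 15 follows it too. The blood count and metabolic panel marked at Visit A supply white cells, hemoglobin, platelets, creatinine, and the transaminases with bilirubin. Sections 13.4.1 and 13.4.2 show that neither panel includes PT or PTT.

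If the schedule is followed as written, a child who already meets the PT/PTT exclusion passes both eligibility checks. That child then receives rituximab, intravenous methylprednisolone and, nominally, about 5 days of sirolimus and prednisolone before the disqualifying result is available. The exposure brings no prospect of gene transfer in that cycle.

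There is also a problem of interpretation. Section 8.2 asks whether a rise in clotting measures has another cause. With no value scheduled before the regimen starts, a high Day -2 result cannot be classed as pre-existing or new.

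**Working it through.** The check is visit-window arithmetic. The plan gives no figure of its own to reproduce.

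**Inputs** (header rows of Tables 14 and 15, the same in both):

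| Visit | Nominal day | Window | Relevant mark |
|---|---|---|---|
| A | -56 (Week -8) | -84 to -28 | Eligibility check; blood draw |
| B | -16 | -21 to -11 | Eligibility check; blood draw |
| C | -7 | -10 to -4 | Immunosuppression starts |
| D | -2 | -3 to -1 | Only pre-dose PT/PTT/INR |

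**Start of immunosuppression to PT/PTT (D minus C)**
- Nominal: -2 - (-7) = 5 days.
- Shortest: -3 - (-4) = 1 day.
- Longest: -1 - (-10) = 9 days.

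The gap is positive for every permitted pair of dates, so no use of the windows brings the scheduled result before the first infusion.

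**Last eligibility check to PT/PTT (D minus B)**
- Nominal: -2 - (-16) = 14 days.
- Shortest: -3 - (-11) = 8 days.
- Longest: -1 - (-21) = 20 days.

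**With the test added at Visit B (C minus B)**
- Nominal: -7 - (-16) = 9 days before immunosuppression.
- Shortest: -10 - (-11) = 1 day.
- Longest: -4 - (-21) = 17 days.

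**With the test added at Visit A (C minus A)**
- Nominal: -7 - (-56) = 49 days before immunosuppression.
- Shortest: -10 - (-28) = 18 days.
- Longest: -4 - (-84) = 80 days.

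Either visit puts the draw ahead of Visit C in every case. At the 1-day minimum from Visit B the result must come back quickly, so the amendment should require the result, not only the draw.

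**Blood volume.** The documents give no tube size. Assuming 1 to 3 mL, and taking the weekly 10 mL figure in the research-blood footnotes as the yardstick, the addition is 1/10 = 10% to 3/10 = 30% of it.

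**The case against.** The strongest reply is that the child is protected where it matters most. PT/PTT is tested before the thalamic infusion and before any vector, and Section 8.2 has a stopping and withdrawal rule that a Day -2 result can trigger. Investigators may order additional safety tests at any time, and the Surgical Manual, which is not among the documents, may call for earlier clotting studies. An abnormality of this size may also be rare.

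Most of this stands. A reader might infer from the timing gap that a child with deranged clotting could reach neurosurgery untested; the documents show the opposite. What remains is that the Section 8.2 rule acts only after the regimen has started, and that extra tests are allowed but not required.

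A reader might also infer a fixed delay to re-entry, because exclusion 14 bars "History of or current chemotherapy, radiotherapy or other immunosuppressive therapy within the past 30 days", which on its face covers the rituximab and sirolimus just given. The documents do not support stating that as a cost. Where the Section 8.2 rule applies, the child is withdrawn. Re-screening in Section 9.1 is for those otherwise eligible but "deemed not currently fit for neurosurgery may be re-screened at the discretion of the investigator", and a child who meets exclusion 15 is not plainly in that group. Exclusion 14 also names no date from which the 30 days are judged. In a repeat cycle, Visit B falls nominally -16 - (-56) = 40 days after Visit A, so if the bar is judged at Visit B or later it may add nothing.

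**Conclusion.** The concern holds as a minor scheduling defect. In both tables the only scheduled pre-dose PT/PTT comes 5 days (1 to 9) after immunosuppression starts and 14 days (8 to 20) after the last eligibility check. A fixed-threshold exclusion therefore cannot be applied from scheduled data before the child is immunosuppressed. The timing rests only on the visit windows and the table marks, and is certain.

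The size of the harm is not known. The documents give no frequency of PT/PTT above twice normal; the number of children affected is probably small. The consequence is avoidable drug exposure and an uninterpretable Day -2 value, not unprotected surgery. No endpoint, estimate or analysis is affected. The finding assumes that sites follow the schedule as written and that no unseen manual requires an earlier test.

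**What to change.** In Tables 14 and 15, add PT/PTT/INR to a blood draw already scheduled at Visit A or Visit B, and state in the footnote that the result must be available and meet exclusion 15 before the first Visit C infusion. Keep the Day -2 draw as the pre-surgical repeat; it then has a baseline for the Section 8.2 rule.

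The documents do not settle which visit is better. Visit A leaves more time to act, but the result could be up to 80 days old at Visit C. Visit B gives a fresher value (1 to 17 days), but its blood is shared with the research samples, whose amount depends on the "overall volume of blood collected within a 1-week period remaining < 10 mL".

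The cost is an amendment to one row and one footnote in each of two tables, plus an assumed 1 to 3 mL of blood. No extra visit or needle stick is needed. Because Table 15 also governs the up to 10 infants planned for Stage 2, the change would apply to them.

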9.3. Participant Withdrawal Criteria

Since AXO-AAV-GM2 is a one-time administration, withdrawal of therapy is not possible.

9.4. Study Stopping Criteria

Temporary suspension of enrollment and administration of AXO-AAV-GM2 to study participants will result if any of the following occur in the study:

- 1. Death of any participant in which the cause of death is assessed by the investigator as at least possibly related to the AXO-AAV-GM2 or the neurosurgical administration procedure.
- 2. Intracranial hemorrhage related to the BiTh procedure or an event suggestive of or consistent with craniospinal herniation related to the ICM/IT procedure.
- 3. Two or more CTCAE Grade 3 or higher adverse events in any participant that are assessed by the investigator as possibly, probably or definitely related to AXO-AAV-GM2 or the neurosurgical administration procedure

Confidential Page 70 of 97

Clinical Study Protocol: AXO-GM2-001

Version 8.0, 09 June 2023

4. An SAE in any participant where the event is assessed by the investigator as possibly, probably or definitely related to AXO-AAV-GM2 or the neurosurgical administration procedure

The DSMC will review all available safety data for AXO-AAV-GM2 and the neurosurgical administration/infusion procedures and will make recommendation(s) regarding further study conduct. The DSMC may make a recommendation regarding dose de-escalation/escalation. The clinical study may resume after appropriate steps are taken to address these AEs, including revision of the clinical protocol. Any participants who have already received IMP and are currently in the study at the time study stopping criteria are met will continue to be followed-up, for safety and any signs of efficacy, per protocol.

Confidential Page 71 of 97

Version 8.0, 09 June 2023

